The subgenual Anterior Cingulate Cortex (sgACC) has been well established as a brain area sensitive to negative mood inductions and is implicated in neural abnormalities associated with affective and stress disorders. It is therefore one of the primary targets for deep brain stimulation (DBS) treatment of MDD using surgically implanted DBS devices. Recent posthoc imaging studies of patients who have undergone TMS treatment for depression suggest that treatment outcomes tended to be better when patients were by chance stimulated in an area of lateral prefrontal cortex that had high levels of functional connectivity with sgACC. Based on this finding, and on our own interleaved TMS/fMRI probe data, we contend that targeting delivery of TMS to the brain surface non-invasively as indicated by sgACC resting functional connectivity may be especially effective in downregulating sgACC and thereby producing superior clinical outcomes. We have used TMS/fMRI to better understand causal communication among circuits typically examined with resting fMRI alone (Chen et al., 2013). Our recent work suggests there are specific sites that, when stimulated, influence subcortical brain areas implicated in affective disorders such as the sgACC. Previously, we targeted TMS based on brain atlases mapped onto individual brain surfaces. This study will utilize individualized targeting from participants' own fMRI scans. We will focus on a target region of the lateral prefrontal cortex (LPFC) that our data suggest is particularly effective at influencing the sgACC. As alternative brain targets, we will also test the efficacy of prefrontal sites with hypothesized connections to downstream depression-related abnormalities. A normal, FDA-approved clinical application of TMS involves long trains of repetitive TMS applied for approximately 40 minutes, 5 days/week, over 2-6 weeks, for a total of 10-30 TMS visits. The present study utilizes the same FDA-approved devices (Magventure Cool-Coil B65, MagVenture X100 Stimulator) to administer TMS. We will be administering brain stimulation in smaller doses as compared with the FDA-approved protocol, but using a well-validated protocol, theta-burst stimulation (Huang et al., 2005), which will result in a reduced number of total pulses delivered to the subject in any given TMS session. This is not a treatment study, and stimulation is not designed to provide treatment in this study. Instead, the TMS delivery is meant to temporarily modify brain circuit communication between the lateral prefrontal cortex and subcortical structures to prove that this pathway can be influenced non-invasively with TMS. In addition to these repetitive TMS protocols, we will perform brief TMS delivery in the MRI machine with a research device (MRI-B91 Air Cooled Coil). We have attached several additional examples of prior studies which have safely utilized TMS outside of its FDA-approved protocol, even in heightened doses. For instance, in prior studies subjects have received the FDA-approved 3000 rTMS pulses, but done bilaterally instead of unilaterally (6000 total stimulations) every weekday over 4-6 weeks (see Bakker et al., 2015). Similarly, subjects have received 3600 rTMS pulses every weekday over 10 days (see Chistyakov et al., 2015), or 3000 rTMS pulses every weekday over 6 weeks (see O'Reardon et al., 2007). Another study applied the FDA-approved protocol in more than a double-dose, with 6800 stimulations to 1 site every weekday over 7 weeks average participation (Hadley et al., 2013). The present study utilizes many fewer stimulations than these other protocols, with each visit including a maximum of 3700 pulses. For additional information, please see Anderson et al., 2006 for demonstrations of the safety of repeated exposure to TMS. Likewise, please see Wagner et al., 2007 and Parkin et al., 2015 for reviews of the importance of TMS research and how our proposed studies fit in the present and growing body of literature.

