
Study Design

Phase*

Not applicable

Design

All subjects will receive active TMS to our novel fMRI-guided targeting method over the course of 3 days, preceded and followed by a 2hr MRI scan during which TMS is administered throughout.

Study duration

Enrollment of subjects in this study will take place over approximately 2 years. Each subject will complete 8 study visits over the course of ~3 weeks. The study schedule is as follows: Visit 1: Consenting / Screening procedures (approx. 3 hours) Visit 2: Baseline MRI Scan to determine TMS targets (1 hour) Visit 3: TMS/ fMRI Scan #1 & Assessments (approx. 3 hours) Visits 4-6: Mini TBS Visits - TMS to the fMRI-guided site (approx. 1hr each) Visit 7: Follow-Up Visit - TMS/fMRI Scan #2 (approx. 3 hours)

Resources necessary for human research protection

Describe research staff and justify that the staff are adequate in number and qualifications to conduct the research. Describe how you will ensure that all staff assisting with the research are adequately informed about the protocol and their research related duties. Please allow adequate time for the researchers to conduct and complete the research. Please confirm that there are adequate facilities for the research.

Staff will be trained on the protocol and inclusion/exclusion criteria. TMS protocols, as well as clinical and neurological assessments, will be administered by specially-trained staff in the Center for Neuromodulation in Depression and Stress the University of Pennsylvania Department of Psychiatry. All TMS staff will be trained by the PI ([name].) and the Center Director ([name].). Other facilities will include various laboratory spaces specializing in advanced computing and analysis of neuroimaging and cognitive datasets. Scans will be conducted on a Siemens Prisma 3 Tesla whole-body MRI with a 64-channel head/neck array, housed in the Center for Advanced Magnetic Resonance Imaging and Spectroscopy (CAMRIS). Additional MRI resources, such as a mock scanner, may be accessed from the Center for Functional Neuroimaging (CfN).

Characteristics of the Study Population

Target population

Patients will be diagnosed with current Major Depressive Disorder as determined by meeting the DSM criteria for MDD; a subset of patients will be diagnosed with current Persistent Depressive Disorder (PDD) instead of current MDD, as per the May 2018 protocol. They will be otherwise healthy, right-handed, adults aged 18-60 years.

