Pre-screening: Participants may complete an online or phone screening form to see if they meet basic eligibility requirements. Screening will include the collection of contact information, basic demographics, and a brief medical and psychiatric history. Screenings will be recorded in REDCap; this data will be retained indefinitely. The screening data will not be used for analyses and will only be retained to help research staff monitor recruitment resources, reasons individuals do not meet eligibility, and to help avoid rescreening the same individuals. We request a waiver of HIPAA authorization for this aspect of the study. Visit 1/ Screening Visit: Informed consent will be obtained upon arrival for an initial visit and before any study-related procedures are conducted. The rest of this screening visit will include a structured diagnostic interview (SCID-5), psychiatric and medical evaluation, collection of demographic information, and a demonstration of TMS. For participants that indicated regular drug use in prescreening or screening forms, we may use a urine drug screen to confirm adherence to study policy of abstinence. The urine drug screen will be collected by study staff; test results will be stored in REDCap and the test destroyed after. The information collected in this initial visit will determine if the subject meets all inclusion criteria. Upon meeting all criteria for inclusion in the study, subsequent dates will be set for the participant to complete all study-related procedures. Visit 2/ Initial MRI Scan: Subjects will complete 60 minutes of structural MRI and resting-state fMRI scans. Structural and functional scans will be obtained in each session on a clinically-approved 3 Tesla Siemens Prisma (Erlangen, Germany) scanner, equipped with 40mT/m gradients and 200 mT/m/s slew-rates, using a Siemens 64-channel head coil. The total time in the scanner will be approximately 60 minutes. Based on our experience, this is well within patients ability to tolerate the scanning procedures without discomfort and without excessive motion. All MRI imaging protocols will be reviewed and approved by CAMRIS. An experienced technician and a member of the study team will be present during the MR session to ensure participant safety and well-being. If the participant complains of feeling claustrophobic and does not wish to complete the MRI, the study will be terminated. Emergency personnel and equipment are immediately available to the MRI room should the need arise. It is possible that during the course of the research study, the research staff may notice unexpected findings on an MRI scan. Should this occur, the findings will be assessed by a trained radiologist. The study doctor will inform research subjects of any significant findings. Visit 3/ TMS + MRI Baseline Scan: Participants will return for a subsequent MRI scan with concurrent TMS brain stimulations. The purpose of this TMS/MRI scan is to probe brain networks prior to the main stimulation protocols, which will occur at the subsequent visits. Brain data from the Initial MRI scan (stimulation target in individualized brain space) will be calibrated with the skin and scalp using a Polaris Vicra camera (Brainsight neuronavigation) to allow marking of the stimulation sites. Our MRI-compatible TMS system (MagPro X100 Stimulator, MRI-B91 TMS coil) is housed in Stellar Chance at the 3-Tesla MRI machine. The apparatus was installed under the supervision of [name]. a member of CAMRIS, and we have attached a signed letter of support from [name] for this protocol. Additionally, participants will complete a series of baseline clinical and neuropsychological assessments. Visit 4-6/ Mini TMS Sessions: Participants will return for 3 consecutive days (+/- 1 day). During each session, subjects will receive theta-burst stimulation (see Huang et al., 2005), which is a slight modification of the FDA-approved protocol for TMS. A normal, FDA-approved clinical application of TMS involves long trains of repetitive TMS applied for approximately 40 minutes, 5 days/week, over 2-6 weeks, for a total of 10-30 TMS visits. We have attached several examples of prior studies which have safely utilized TMS outside of its FDA-approved protocol, even in heightened doses. Our study uses many fewer stimulations than these studies, and we are using the FDA-approved devices for treatment of depression in this protocol (MagPro X100 Stimulator, Cool-Coil B65 TMS coil). Please see the "Background" for more details. Patients will additionally complete a few brief assessments at these visits. Visit 7/ TMS + MRI Scan #2: This visit will mirror Visit 3, the baseline visit. There will be a 2-hour MRI/TMS scan and subjects will complete the same set of clinical and neuropsychological assessments from Visit 3.

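### Does in-scanner TMS described both as brief and as running throughout a 2-hour scan, under a single 3700-pulse ceiling, call for a change to the plan?

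*Combined protocol and SAP*

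**What the plan says.** - **Background**, on delivery in the scanner: "In addition to these repetitive TMS protocols, we will perform brief TMS delivery in the MRI machine with a research device".
- **Study Design, Design**, on the three stimulation days: "preceded and followed by a 2hr MRI scan during which TMS is administered throughout".
- **Study Procedures, Procedures**, on the purpose of the Visit 3 scan: to "probe brain networks prior to the main stimulation protocols, which will occur at the subsequent visits". On Visit 7: "This visit will mirror Visit 3, the baseline visit", and "There will be a 2-hour MRI/TMS scan".
- **Background**, on the amount: the study is said to use many fewer stimulations than the cited protocols, "with each visit including a maximum of 3700 pulses".
- **Background**, on theta-burst compared with the approved protocol: smaller doses, "which will result in a reduced number of total pulses delivered to the subject in any given TMS session".
- **Background**, on the approved figure, in describing an earlier bilateral study: "subjects have received the FDA-approved 3000 rTMS pulses". An approved course is put at 10 to 30 visits.

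The secondary outcome (Objectives) is the change in functional brain activity after the three-day regimen. The visible text gives no pulse count, rate or train length for the scan and no count for a theta-burst session.

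**The concern.** A reader who meets *brief* in one section and *throughout* a 2-hour scan in the next will ask which is meant, and the one pulse figure does not settle it. Assigned to the theta-burst visits, 3700 exceeds the approved 3000 and sits badly with the claim of fewer pulses per session. Assigned to the scan visits, it makes the probe larger than any session of the main stimulation.

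Two things would be at stake. First, the secondary outcome is read as the effect of the three theta-burst days. If the Visit 3 probe is itself a large dose, the change from Visit 3 to Visit 7 follows four stimulation visits rather than three. Second, the share of stimulation given through the research coil cannot be worked out from the visible text.

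**Working it through.** The figure of 3700 cannot be rebuilt, because the documents give no pulses per train or trains per visit. It can be compared with the other figures in Background.

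1. **Ceiling against the per-session comparators.** 3700/3000 = 1.233, or 23.3% above the approved session. 3700/3600 = 1.028, or 2.8% above the cited 3600-pulse protocol. 3700/6000 = 0.617, or 38.3% below the bilateral protocol. 3700/6800 = 0.544, or 45.6% below the largest one.

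2. **Ceiling against course totals.** Five TMS visits are listed (3 to 7), so the most the plan allows is 5 × 3700 = 18,500. An approved course is 10 × 3000 = 30,000 to 30 × 3000 = 90,000. The cited 3600-pulse protocol gives 3600 × 10 = 36,000. The claim of many fewer stimulations is therefore true per course; per visit it fails against 3000 and 3600.

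3. **Ceiling assigned to the scan visits.** Two hours is 7200 s, and 7200/3700 = 1.95 s per pulse on average (3700/120 = 30.8 per minute). That agrees with *throughout*. The statement about fewer pulses concerns theta-burst and holds if Visits 4 to 6 stay below 3000. Only *brief* is strained, and it has no number to test against.

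4. **Ceiling assigned to the theta-burst visits.** The 23.3% excess in step 1 then conflicts with the statement about fewer pulses. This is the one numerical tension, and it depends on the assignment. A maximum is also an upper bound, not the amount delivered.

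5. **Visit 3 as a share of the pulses before the Visit 7 scan.** With s pulses in the scan and b per theta-burst session, the share is s/(s + 3b).
   - All visits at the ceiling: 3700/(3700 + 11,100) = 3700/14,800 = 25.0%.
   - Scan at the ceiling, theta-burst just under 3000: 3700/(3700 + 3 × 2999) = 3700/12,697 = 29.1%.
   - Scan at one tenth of the ceiling (an assumption, for illustration), same theta-burst: 370/(370 + 8997) = 370/9367 = 4.0%.

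   The larger shares are not floors. They require the scan to deliver the full 3700, which the documents do not say. As s falls towards 0, so does the share.

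6. **Research-coil exposure.** The ceiling covers each visit, so Visits 3 and 7 together are bounded at 2 × 3700 = 7400 pulses. The split is not given, but the exposure is bounded.

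**The case for a change.** The strongest case for a change is that the conflict of description needs no assumption: one section says *brief*, another says *throughout*, and nothing visible reconciles them. The Procedures section also presents the scan as a probe ahead of the main stimulation, so a scan that out-pulses every theta-burst session would strain two descriptions, not one. With every subject on active TMS, nothing separates the probe from the regimen, and a short table of pulses by visit type would cost almost nothing.

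Part of this stands. The wording is loose, the split is absent from the visible text, and a per-visit ceiling of 3700 does not by itself support a claim of fewer pulses than 3000 per session.

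The rest does not carry. *Main* can describe purpose (probe as against regimen) and need not rank the visits by pulse count. Background mentions the team's own interleaved TMS/fMRI probe data, and short deliveries spaced through a scan are individually brief while occurring throughout. Pulse shares also treat probe pulses and theta-burst pulses as interchangeable, whereas Background sets the in-scanner delivery apart from the repetitive protocols. Finally, a table would not repair attribution. The Visit 3 to Visit 7 change is uncontrolled because there is no comparison condition, and that remains so whether the probe is 4% or 29% of the earlier pulses.

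**Conclusion.** This is a gap in wording that the study team can fill from its own stimulation settings; it is not a fault in the design or analysis. Following the plan as written yields the same scans, the same two time points and the same analysis whichever reading is correct. No pulse count enters the outcomes or the Analysis Plan, Visit 7 repeats Visit 3, and it remains literally true that Visit 7 comes after the three-day regimen.

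The size of the tension is 23.3% above 3000 if the ceiling describes the theta-burst visits, and no numerical conflict if it describes only the scan visits. The second reading assumes that Visits 4 to 6 stay below 3000, which the visible text neither states nor denies. The consent form and other attachments were not available and may give the split.

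The Background, Design and Procedures passages need to be reconciled on in-scanner delivery and on which visits the ceiling covers. That is editorial, has no demonstrated effect on a result, and implies no view on the right number of pulses.

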There are no documents attached for this item.

Department budget code

None

Multi-Center Research

Penn as lead

1. Is this a multi-center study where Penn is serving as the Lead Site or the Penn PI is serving as the Lead Investigator?

No

Management of Information for Multi-Center Research**Penn irb of record**

2. Is this a multi-center study where the Penn IRB will be asked to serve as the IRB of Record for other external study sites?

No

Other Sites

No other sites

Protocol

Abstract

Non-invasive transcranial magnetic stimulation (TMS) is now FDA-approved for the treatment of major depressive disorder (MDD). However, there is growing evidence that the targeting strategy for

delivering TMS treatment would yield superior clinical outcomes if it were more tailored to individual neuroanatomy. In this study, we plan to examine whether functional MRI-guided TMS might be effective at temporarily influencing neural circuit communication. If this is true, future studies may utilize these methods to yield an even greater leap forward in promoting optimal clinical outcomes using full doses of TMS for treatment.

Objectives

Overall objectives

We aim to establish the efficacy of TMS stimulation at probing and temporarily influencing brain activity using targets defined by resting connectivity in MDD patients. We hypothesize that fMRI-guided TMS will be effective in modulating the connectivity of neural circuits.

Primary outcome variable(s)

Functional brain activity due to TMS performed at an fMRI-guided brain target

Secondary outcome variable(s)

Changes in functional brain activity after the 3 day stimulation regimen

Background

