Subjects enrolled by Penn Researchers

95

Subjects enrolled by Collaborating Researchers

0

Accrual

All recruitment will be conducted through the University of Pennsylvania and surrounding community to find 40 individuals with MDD to complete the study with usable data. It is assumed that there will be approximately 55 participants who screen fail, are lost to follow up, withdraw, or complete without usable data. Therefore, we estimate that we will need to consent/enroll up to 95 participants overall, in order to adequately test the hypotheses.

Key inclusion criteria

1. 18-60, male or female, inclusive 2. Meets DSM-5 criteria for major depressive disorder (MDD) 3. Capacity to give informed consent and follow study procedures 4. Sufficient command of English language to understand and respond to written as well as verbal instructions 5. Right- handed

Key exclusion criteria

1. Significant disability (e.g., intellectual disability, blindness, deafness, etc.) that would interfere with testing procedures
2. MRI contraindications (e.g., foreign metallic implants, pacemaker, shrapnel or other metal in/on the body that cannot be removed, claustrophobia, etc.)
3. Additional TMS contraindications (e.g., seizure disorder, CNS active disorder, etc.)
4. Medication use that substantially reduces seizure threshold to TMS (olanzapine, chlorpromazine, lithium) and unwilling or unable medically to safely withdraw, at least two weeks prior to TMS, from these medications
5. Opiate medication, antihypertensive medication, or any medication that interferes with blood flow (interferes with fMRI recordings)
6. Current use of psychiatric medication, and unable/ unwilling to safely withdraw 2 weeks prior to study
7. Known neurological disorders (e.g., multiple sclerosis, encephalopathy, seizure disorder, brain tumors, etc.)
8. Diagnosis(es) of an exclusionary DSM-5 Diagnosis, including (but not limited to) bipolar disorder, schizophrenia, current severe substance use disorder, or any other diagnosis as determined by PI.
9. Refusal to abstain from illicit drug use for duration of the study
10. Refusal to abstain from alcohol within 24 hours of scans
11. Woman who is pregnant, breastfeeding, or trying to become pregnant (based on woman's attestation alone)
12. Any other factor that the investigator decides may affect patient safety or compliance (e.g., distance greater than 100 miles from procedure site)

Vulnerable Populations

Children Form

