
The following documents are currently attached to this item:

There are no documents attached for this item.

Deception

Does your project use deception?

No

International Research

Are you conducting research outside of the United States?

No

Analysis Plan

Clinical outcome will be evaluated on symptom scales in a TMS target x Time ANOVA. Similarly, rate of change (slope) x TMS Target will indicate how rapidly each round of stimulation influences symptoms.

The following documents are currently attached to this item:

There are no documents attached for this item.

Data confidentiality

- Paper-based records will be kept in a secure location and only be accessible to personnel involved in the study.**
- Computer-based files will only be made available to personnel involved in the study through the use of access privileges and passwords.**
Prior to access to any study-related information, personnel will be required to sign statements agreeing to protect the security and confidentiality of identifiable information.
- Wherever feasible, identifiers will be removed from study-related information.**
A Certificate of Confidentiality will be obtained, because the research could place the subject at risk of criminal or civil liability or cause damage to the subject's financial standing, employability, or liability.
- A waiver of documentation of consent is being requested, because the only link between the subject and the study would be the consent document and the primary risk is a breach of confidentiality. (This is not an option for FDA-regulated research.)**
- Precautions are in place to ensure the data is secure by using passwords and encryption, because the research involves web-based surveys.**
Audio and/or video recordings will be transcribed and then destroyed to eliminate audible identification of subjects.

Subject Confidentiality

Patients entering the study will be given a unique identifying code. This code will be used on all data obtained from scans or the medical record. Everything will be immediately coded and this coded information will be stored in secure cabinets inside locked rooms or in password protected, IRB compliant online databases, such as REDCap. Any documents connecting the code with the participant name will also be stored in secure cabinets inside locked rooms or in password protected, IRB compliant online databases, such as REDCap.

Sensitive Research Information*

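### The symptom analysis is an ANOVA with no defined analysis set, so change could rest on completers only; a mixed model on all available data is better and costs almost nothing

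*Combined protocol and SAP*

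**What the plan says.** - **Accrual.** The aim is "to find 40 individuals with MDD to complete the study with usable data". The rest are pooled as "approximately 55 participants who screen fail, are lost to follow up, withdraw, or complete without usable data", and the section concludes that "we will need to consent/enroll up to 95 participants overall, in order to adequately test the hypotheses". Losses are not split by cause or by visit, and usable data is not defined.
- **Analysis Plan.** The whole plan is two sentences: "Clinical outcome will be evaluated on symptom scales in a TMS target x Time ANOVA", and a second analysis in which "rate of change (slope) x TMS Target will indicate how rapidly each round of stimulation influences symptoms". Neither sentence states the type of ANOVA, how the slope is fitted, or what happens to a missing visit.
- **Objectives.** The primary outcome is "Functional brain activity due to TMS performed at an fMRI-guided brain target" and the secondary is "Changes in functional brain activity after the 3 day stimulation regimen". No analysis method is given for either.
- **Procedures.** Clinical assessments and a TMS/fMRI scan take place at Visit 3, brief assessments at Visits 4 to 6, and the Visit 3 set is repeated at Visit 7. Of the Visit 3 scan the protocol says: "The purpose of this TMS/MRI scan is to probe brain networks prior to the main stimulation protocols".
- **Design.** All subjects receive active TMS; there is no control arm.

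**The concern.** Symptoms are followed over up to five visits, and the slope sentence implies symptom data after each round of stimulation. Someone who stops after one or two theta-burst sessions therefore leaves informative data. The named method, in its classical form, cannot use an incomplete record. The only sample-size statement in the protocol also counts only people who finish with usable data. Together these point towards an analysis of completers, and nothing in the plan steers away from it.

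Two things are at stake. First, if people who feel no benefit or feel worse are more likely to stop, the completers' mean change looks better than that of everyone stimulated, and there is no control arm in which similar loss could offset it. Second, with no rule in place, the choice to keep or drop partial records could be made after the results are known. A smaller matter is efficiency: a usable Visit 3 scan from someone who never reaches Visit 7 still informs the primary outcome if that outcome is read from Visit 3.

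**Working it through.** **1. The plan's own figure.** 40 completers + 55 others = 95, as stated. 55/95 = 57.9% are expected not to give complete usable data. This includes screen failures, who have no post-baseline data, so it is not a drop-out rate. The target of 40 cannot be re-derived, because no alpha, power, effect size or SD is given.

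**2. Unknown quantity.** Let k be the number lost after Visit 3. The documents do not give it. Assumed values: k = 5, 10, 20, so that n = 40 + k start and the proportion staying is p = 40/(40 + k) = 0.889, 0.800, 0.667.

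**3. Completer bias by formula.** Assume that staying is set by a normal propensity with correlation r to the change score. The bias, in SD of the change, is r x φ(c)/p, with c = Φ⁻¹(1 − p). The factor φ(c)/p is 0.213, 0.350 and 0.545 for the three values of k.

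| r | k = 5 | k = 10 | k = 20 |
|---|---|---|---|
| 0 | 0 | 0 | 0 |
| 0.1 | 0.02 | 0.03 | 0.05 |
| 0.3 | 0.06 | 0.11 | 0.16 |
| 0.5 | 0.11 | 0.18 | 0.27 |

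**4. Does a mixed model help?** Simulation, all inputs assumed: five time points, true mean change −0.5, subject intercept SD 1, slope SD 0.6, residual SD 0.3, 60 runs per scenario. In the response-dependent case the k subjects with the least early improvement all leave after the third time point, which is a deliberately strong mechanism.

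| Loss | k | Full sample | Completers | Mixed model, all data |
|---|---|---|---|---|
| Unrelated to response | 10 | −0.50 | −0.51 | −0.51 |
| Response-dependent | 10 | −0.49 | −0.66 | −0.48 |
| Response-dependent | 20 | −0.50 | −0.77 | −0.50 |

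The run-to-run SD is about 0.1, so each mean has a Monte Carlo error of about 0.1/√60 = 0.013. A second assumed design had no true change, a within-person correlation of 0.5 to 0.7, drop-out more likely after worsening, and 11 to 24% lost. It gave completers a spurious improvement of 0.04 to 0.17 SD, and all-data estimates within 0.01 SD of zero.

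**5. Limit for pre/post imaging.** TMS/fMRI scans exist only at Visits 3 and 7. Under the same kind of worsening-driven loss (9 to 25% lost), completer bias was 0.04 to 0.16 SD, and a mixed model on the two scans alone still left 0.03 to 0.08 SD. The model cannot see what happened between the scans.

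**6. Visit 3 scans and the primary outcome.** For a one-sample mean the standard error scales as 1/√n. With 4 to 12 extra usable scans (assumed), √(40/44) = 0.953 and √(40/52) = 0.877, a cut of about 5 to 12%. At an assumed two-sided 5% level and 80% power, the detectable standardised effect moves from 0.45 (n = 40) to 0.43 (n = 44) or 0.40 (n = 52).

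**The case against.** A reader might infer that the plan discards usable Visit 3 scans and partial courses, and so does bias the result. The documents do not support that. The figure of 40 is a recruitment target and does not define an analysis set, and nothing in the protocol excludes partial data. The ANOVA is assigned to symptom scales only, so it cannot remove a scan; the imaging outcomes have no stated analysis at all. The slope x target analysis could use partial courses, depending on how it is fitted. Many of the 55 may be screen failures with nothing to lose.

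Three further points have weight:
- Symptom change is neither the primary nor the secondary outcome, and the Background says that this is not a treatment study.
- Every bias figure rests on an assumed loss mechanism. In the simulations the mixed model does well because drop-out depends on data that it can see.
- The Objectives do not tie the primary outcome to Visit 3. Reading it from that visit alone is reasonable but not stated.

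These limit the claim to a risk that the plan leaves open. They do not defend the ANOVA. The protocol plans two symptom analyses over repeated visits, the method it names handles missing visits poorly in its classical form, and a better method needs no extra data.

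**Conclusion.** The concern holds as a choice of method with a missing analysis set, and not as a demonstrated bias. A classical target x Time ANOVA would rest symptom change on people with every visit. The resulting bias is zero if loss is unrelated to response. It is about 0.06 to 0.16 SD of the change if 5 to 20 people are lost after Visit 3 and change and staying correlate at 0.3. Both the number lost and the correlation are assumptions. A mixed model on all available data removes this bias when loss depends on recorded symptoms. It removes only part of it for the two-scan imaging change. The gain from keeping every usable Visit 3 scan is small and also rests on an assumed count. The change is worth making because it is cheap and fixes the rule before results are seen.

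**What to change.** 1. **Symptom scales.** Replace the ANOVA by a likelihood-based mixed model with visit as a categorical factor and a subject random effect. Keep the TMS target factor and its interaction with time if more than one target is used. Include everyone who received at least one theta-burst session, and fit the slope analysis on the same data. Report completers as a sensitivity analysis.
2. **Primary imaging outcome.** Where it is estimated from the Visit 3 scan, include every usable Visit 3 scan whether or not Visit 7 was reached. Define usable before the data are analysed.
3. **Pre/post imaging.** Use all available scans. State that drop-out driven by events between the scans is not fully corrected.
4. **Reporting.** Split the roughly 55 non-contributors into those lost before and those lost after stimulation began, with reasons.

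The cost is wording in the analysis plan; no new data or visits are needed. The downside is that the mixed model relies on data being missing at random. That cannot be verified, but it is a weaker assumption than the one a completer analysis needs.
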